2. HYPOTHESES AND SPECIFIC AIMS

The following hypotheses will be tested in this longitudinal study.

A. Hypotheses:

- 1. The finding of an isolated heterogeneous echo pattern in the liver on abdominal ultrasound (US) will predict an increased risk for the subsequent development of cirrhosis in children with cystic fibrosis.
- 2. There will be serum or plasma biomarkers that predict the development of cirrhosis in an individual.
- 3. There will be genetic modifiers that influence the development of cirrhosis.
- 4. There will be no effect on the quality of life, pulmonary or nutritional status of subjects by the finding of an isolated heterogeneous, homogeneous or cirrhosis echo pattern of the liver on abdominal US.
- 5. Doppler analysis of the hepatic and splenic vessels will be a better predictor than gray scale abdominal US alone to predict an increased risk for the subsequent development of cirrhosis
- 6. Cirrhosis incidentally discovered on screening ultrasound progresses slowly and does not result in complications of portal hypertension or hepatic synthetic failure during study follow up.
- 7. Homogeneous liver on ultrasound does not progress to heterogeneous liver or cirrhosis during study follow up.

These hypotheses will be tested by addressing the following Specific Aims.

B. Specific Aims:

The specific aims for this study are:

- 1. To determine if sonographic findings predict the risk of progression of liver disease to cirrhosis by comparing CF subjects with heterogeneous echogenicity pattern on US to those with normal echogenicity pattern on US
- 2. To develop a data and biorepository of serum, plasma, urine and DNA to aid the investigations in ascertaining the mechanisms, consequences, genetic risk factors and biomarkers for the development of cirrhosis
- 3. To determine if there are differences in health related quality of life, pulmonary or nutritional status in children with CF who have a heterogeneous, homogeneous or cirrhosis echo pattern on US compared to those who have a normal echo pattern on US
- 4. To determine if Doppler velocity measurements of hepatic and splenic vessels predict an increased risk for the development of cirrhosis and to characterize these parameters and their progression in children with cirrhosis at screening.
- 5. To determine if subjects with cirrhosis discovered in this study develop portal hypertension, complications of portal hypertension or worsening hepatic synthetic function during the study.

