4.2 Enrollment

The study population will consist of males and females 3 through 12 years of age with Cystic Fibrosis and pancreatic insufficiency. All racial and ethnic groups will be included. All current and newly diagnosed patients (based on diagnostic and enrollment criteria) with Cystic Fibrosis 3 through 12 years of age who are enrolled in the CF Registry Study or the Toronto CF Registry and followed at each CFLD-NET Clinical Site will be offered enrollment into this study. Pulmonary and nutritional outcomes will be derived from CF Registry study data, thus the requirement for enrollment in the CF Registry.

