During the duration of this study, the plan is to enroll study participants at all of the Clinical Sites: There will be approximately 800 subjects enrolled. Subjects will be assigned to one of four groups based on their US findings at entry: heterogeneous (HTG) pattern (Group A: HTG US), normal (NL) pattern (Group B: NL US), cirrhosis (Group C) or homogeneous pattern (Group D). Approximately 60 subjects with a heterogeneous echo pattern of the liver (HTG) on abdominal ultrasound (Group A: HTG US) will be enrolled. These study participants will be matched (one to two by age, center, and *Pseudomonas aeruginosa* status) to subjects from Group B (NL US). Subjects from Group B who are not matched to a subject in Group A will only have a single screening visit. The study will continue to enroll patients until we accrue 60 matched trios (HTG US and 2 NL US). Thus recruitment for this study will stop when 60 matched trios are enrolled. Please see Section 6.1 for more information.

- Group A Approximately 60 subjects with a heterogeneous echo pattern of the liver on abdominal ultrasound (HTG US).
- Group B Approximately 680 subjects with a normal echo pattern on abdominal ultrasound (NL US). Of these subjects, approximately 120 will be matched 1 from Group A:2 from Group B and followed for the duration of the study. The remaining unmatched subjects will not be followed beyond their initial visit.
- Group C-subjects with cirrhosis found on ultrasound will be followed for the duration of the study with yearly visits and bi-yearly ultrasounds. We estimate that 30 subjects will be in this group.
- Group D- subjects with homogeneous liver on ultrasound will also be followed with yearly visits and biyearly ultrasounds for 5 years. We estimate that 30 subjects will be in this group

Subjects who previously participated in the study and were found to have cirrhosis or homogeous liver and thus exited the study or normal US pattern and are potential matches, can be re-contacted and re-consented for continued participation in the study without repeating the screening ultrasound.

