4.32 Screening Visit

This visit would occur in conjunction with a routine clinical visit. Studies performed for this visit would include:

- 1. Consent/assent procedures
- 2. Eligibility: Assessment and documentation of the Inclusion and Exclusion Criteria
- 3. Review of diagnosis of CF (genotype data and sweat chloride data); Confirmation of CF diagnosis
- 4. Review of the medical record for evidence of pancreatic insufficiency.
 - Assessment for pancreatic insufficiency:
 - a. Genetic testing: prior genetic testing for CFTR mutations (if performed previously)
 - b. Fecal elastase (if previously done)
 - c. 72 hour fecal fat (if previously done)
- 5. Data:
 - a. For Matching: DOB, Center, Pseudomonas status
 - b. Other data: Race, CF Registry patient number, genotype (DeltaF508 homozygous, heterozygous and other).
- 6. Quality of Life (All patients at Screening to assure that this is performed before the results of the US are known)
 - a. CFQ-R Preschool Version (3-6 years old)
 - b. CFQ-R Child Version (6-13 years old)
 - c. CFQ-R parent Version (6-13 years old)
 - d. CFQ-R Teen Adult (14 and up)
 - e. CFQ-R Preschool version (3-5 years old)
 - f. PEDS QL Child Report (8-12 years old)
 - g. PEDS QL Parent Report (3-12 years old)
- 7. Abdominal US: Performed per study protocol at the center. [This would be a research study]. This may be obtained at any time in the seven months after consent has been given. Classification of the US findings will be based on the consensus of 3 study radiologists (one of these will be from the center that performs the US). All readings should be completed within approximately 4 weeks. Those with an isolated heterogeneous echogenicity pattern would be assigned to Group A (HTG US) and those with a normal echogenicity pattern would be assigned to Group B (NL US). Those with cirrhosis would be assigned to Group C and those with homogeneous echogenicity to Group D. Group A (HTG US) subjects will be matched to 2 Group B subjects (within 6-12 months of enrollment) and followed for approximately six years, through the completion of the Year 6 US and study closeout procedures. In the event that a match cannot be found for a Group A subject (HTG US) within six months of enrollment, the matching criteria will be relaxed sequentially using the algorithm specified in the Manual of Operations (MOO). All participants with a HTG US (whether matched or not), will be followed annually.

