Group B (NL US) subjects matched 2 from Group B to one from Group A subject will be followed for approximately six years, through the completion of the Year 6 US and study closeout procedures. Group B subjects who are not utilized as Group A controls, will have an initial visit and no subsequent visits. However, their baseline data will be maintained to allow determination of associations with US findings.

Group C (cirrhosis) and D (homogeneous liver) will be followed annually with visits and bi-yearly with ultrasound.

(Patients not enrolled in the longitudinal follow up component of the study, will not be followed, but we will request permission to re-contact the subject in the consent for this study.)

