6.2. Analysis Plan

Outcome Variables

The specific aims of this study are to determine if imaging changes identified by ultrasound (US) predict the risk of progression of liver disease by comparing subjects with heterogeneous livers to those with normal livers.

The Primary Outcome is the development of cirrhosis

• Cirrhosis will be defined by imaging criteria (Grade 3 or 4 as described in 4.4 Section on US Grading) in group A or B

Secondary outcomes relate to effect on associated pulmonary and nutritional issues, signs and symptoms of portal hypertension and markers of hepatic synthetic function:

- Health related quality of life
- Growth (length, weight and BMI Z-score, anthropometrics)
- AST, ALT, GGTP
- FEV1, FVC
- Sputum Culture (Pseudomonas, Burkholderia cepacia)
- Use of IV antibiotics
- Hospitalization for treatment of pulmonary exacerbation
- CBC (WBC, Hbg, ANC, platelet count)
- Fat soluble vitamin levels (Vitamin E, 25 hydroxy vitamin D, Vitamin A)
- Appearance of signs or symptoms of portal hypertension among children with cirrhosis discovered during the study, including ultrasound findings and clinical symptoms
- Development of cirrhosis amongst children with homogeneous echogenicity at screening

Prediction of Cirrhosis from US: Chi square test of independence, logistic regression and multiple logistic regression will be used to assess the odds of developing cirrhosis between those with heterogeneous livers (Group A compared with patients with normal livers (Group B). Since data will be collected longitudinally, Cox Regression with time dependent covariates will also be used to examine time to onset of cirrhosis.

Analysis of Secondary outcomes: Mixed model longitudinal data analysis will be used to compare Group A and Group B over time on health related quality of life, growth (length, weight and BMI Z-score, anthropometrics, body composition), AST, ALT, GGTP, PT, INR, FEV1, rate of change in other PFTs, CBC (WBC, platelet count), spleen size on ultrasound and fat soluble vitamin levels. Logistic regression and general estimating equations will be used to compare results of Sputum Culture (Pseudomonas), use of IV antibiotics, and hospitalization for treatment of pulmonary exacerbation.

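### Followed normal controls are matched to heterogeneous children on screening Pseudomonas status, and Pseudomonas culture is then compared between the same groups, so a null culture result cannot by itself support Hypothesis 4

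*Protocol*

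**What the plan says.** - **Matching.** Section 4.24 pairs each Group A child with two Group B children by age, center and Pseudomonas aeruginosa status. Section 4.32 takes these variables at the screening visit: "For Matching: DOB, Center, Pseudomonas status". If no match is found within six months, the criteria are relaxed in an order set in the Manual of Operations. Every heterogeneous child is followed, matched or not.
- **Who is followed.** Sections 4.24 and 4.32 follow only the matched normals, about 120 of about 680. The others have one visit, but "their baseline data will be maintained to allow determination of associations with US findings".
- **The question.** Hypothesis 4 in section 2 reads: "There will be no effect on the quality of life, pulmonary or nutritional status of subjects". Aim 3 asks whether children with an abnormal pattern differ in these respects from children with a normal one.
- **The analysis.** Section 6.2 lists sputum culture, FEV1 and FVC, IV antibiotics and hospitalization for pulmonary exacerbation as secondary outcomes. Mixed models compare Groups A and B over time on the continuous ones. For the binary ones, logistic regression and "general estimating equations will be used to compare results of Sputum Culture (Pseudomonas), use of IV antibiotics", along with hospitalization. The section ends by promising descriptive statistics on each secondary outcome for each of the four screening groups.

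**The concern.** Pseudomonas status is both a criterion for choosing the controls and an outcome on which they are compared. If the match is achieved, Groups A and B have the same proportion positive at entry whatever the truth among children with these patterns. Infection can persist, so part of that imposed equality carries into the early follow-up visits. Section 6.2 does not allow for this.

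Hypothesis 4 predicts no difference, so the design leans toward the stated expectation. A null culture result could be reported as support for the hypothesis when control selection helped to produce it. Aim 3 also asks about children with a normal pattern, not about normals chosen to share the cases' infection status. Matching on Pseudomonas may be sensible for the cirrhosis comparison; the difficulty is confined to reusing the matched set for this outcome.

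**Working it through.** The plan states no figure on this point, so there is none to reproduce. The entry result needs no arithmetic: exact matching on a yes/no status makes the entry difference in that status zero. The model below shows only how the effect could carry forward. **All its rates are assumptions**, because the protocol gives no Pseudomonas prevalence, acquisition or persistence.

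**Model.** Let p(t) be the proportion positive in year t, s the yearly persistence and q the yearly acquisition:

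p(t+1) = p(t)·s + (1 − p(t))·q

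Assumed at entry: Group A 40%, all normals 30%, matched normals 40% (equal to Group A by selection).

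**Year 1 with s = 0.8 and q = 0.15 (A) or 0.10 (normals):**
- Group A: 0.40×0.8 + 0.60×0.15 = 0.41
- All normals: 0.30×0.8 + 0.70×0.10 = 0.31, difference 10 points
- Matched normals: 0.40×0.8 + 0.60×0.10 = 0.38, difference 3 points

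**Continued to Year 6, with means over entry and Years 1 to 6:**

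| Acquisition A / normals | s | Mean difference, all normals | Mean difference, matched normals | Year 6, all | Year 6, matched |
|---|---|---|---|---|---|
| 15% / 10% | 0.8 | 9.9 points | 5.5 | 9.7 | 8.5 |
| 15% / 10% | 0.9 | 11.4 points | 5.7 | 11.7 | 9.1 |
| 10% / 10% | 0.8 | 4.4 points | 0 | 1.2 | 0 |
| 10% / 10% | 0.9 | 5.6 points | 0 | 2.6 | 0 |

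With unequal acquisition, the matched mean is 50–56% of the unmatched mean, but by Year 6 the matched difference is 78–88% of the unmatched one. The loss therefore falls at entry and in the early years.

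**Other assumed values** (entry 40–50% against 30–40%, persistence 60–80%) give the same pattern. With equal acquisition, a mean difference of 2.8–8.7 points becomes 0. With 15% against 10% acquisition, 7.5–13.8 points becomes 4.6–5.5.

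**Related outcomes.** Suppose 50% of positive and 20% of negative children receive IV antibiotics (assumed). The part of the entry difference that runs through Pseudomonas is (0.50 − 0.20) × (difference in positivity): 0.30×0.10 = 3 points, or 0.30×0.20 = 6 points. Matching sets this part to 0. Any effect by another route is untouched.

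**The case against.** The best defence is that matching fixes only the screening value, while section 6.2 compares groups over time. Making groups alike at entry and then comparing their later course resembles baseline adjustment. If the effect in Hypothesis 4 means later course, the zero under equal acquisition is the right answer, because that difference existed before follow-up began. This is a fair reading of the hypothesis. It does not serve Aim 3 read cross-sectionally, and it would still require section 6.2 to say that its culture comparison is conditional on entry status.

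A reader might infer that the design guarantees a null pulmonary result, or that equality is imposed at every visit. The documents do not support either:
- Matching can be relaxed and unmatched heterogeneous children stay in follow-up, so balance may be incomplete.
- Differences in acquisition can still emerge, as the Year 6 figures show.
- Nothing in the protocol shows that the groups differ in Pseudomonas at entry. If they do not, nothing is lost.
- For FEV1, IV antibiotics and admissions, the push is toward no difference only if the Pseudomonas route acts in the same direction as any other effect.

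A reader might also infer that the unmatched normals have no place in section 6.2. Its closing descriptive statistics cover Group B as defined by the screening ultrasound, and section 4.32 keeps the unmatched children's baseline data for associations with ultrasound findings. A descriptive entry comparison is thus available; a formal one is not specified.

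Finally, analysis sets and covariates often belong in a statistical analysis plan, which is not at hand. But the protocol itself fixes the matching variable, the outcome and the A-against-B comparison, and the conflict lies among those three.

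**Conclusion.** The point holds in limited form. To the extent that matching is achieved, the A–B difference in Pseudomonas culture is removed at entry by selection and attenuated in early follow-up, fading as new acquisition accrues. A null culture result in the matched set cannot by itself support Hypothesis 4.

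The size cannot be known from the protocol. The roughly halved mean difference in the illustration rests on the assumed rates and exact matching, and on averaging in the entry zero and the early years.

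The reach is narrow. FEV1, IV antibiotics and pulmonary hospitalization lose only the component acting through entry Pseudomonas status. Quality of life and growth are not matching variables, Groups C and D are unmatched, and the primary cirrhosis outcome is unaffected. The change is still worth making, since it is cheap and bears directly on how a secondary hypothesis of no effect will be read.

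**What to change.** Leave the matching unchanged and amend section 6.2:

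1. **Entry comparison.** For the cross-sectional part of Aim 3, formally compare entry Pseudomonas status, and other entry measures available at screening or from the Registry, between the pattern groups and all Group B children. Include the roughly 560 unmatched (680 − 120). Adjust for age and center but not for Pseudomonas. Section 4.32 already records Pseudomonas status, quality of life and Registry number for everyone at screening, and section 4.2 says: "Pulmonary and nutritional outcomes will be derived from CF Registry study data". For an A–B difference in means with equal variance, using 680 rather than 120 normals multiplies the standard error by √(1/60 + 1/680) / √(1/60 + 1/120) = 0.135/0.158 = 0.85, before adjustment.
2. **Follow-up culture.** Analyse new acquisition among children negative at entry, or use a model conditional on entry status that keeps all children.
3. **Reporting.** Describe matched-set contrasts in culture, FEV1, IV antibiotics and hospitalization as conditional on entry Pseudomonas status, and do not take a null culture contrast alone as evidence for Hypothesis 4.

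The cost is analysis wording and a Registry pull for the unmatched normals. If only acquisition is analysed, children positive at entry drop out of that analysis; the conditional model avoids this.

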7. DATA MANAGEMENT

7.1 Case Report Forms

The Data Coordinating Center at the University of Michigan is responsible for data management and analysis. It is the data coordinating center for several multi-center trials. Case report forms are developed by the data coordinating center (DCC) and published on the CFLD-NET password-controlled website. The case report forms do not contain any personal subject identifiers, except dates, such as date of birth (which will be converted to age prior to storage in the NIDDK repository), which are necessary for research purposes. As needed, the coordinator prints the forms for each subject. A combination of webenabled and centralized data entry and management will be used. After the case report forms for a visit are completed, the research coordinator will enter a limited set of data into a web-enabled data management system. Original case report forms will be securely maintained at the clinical sites. Clean copies of the case report forms will be sent monthly by overnight carrier to the DCC where they will be entered into the database using double entry. The forms entered by the coordinator (except for those containing personal identifying information) will also be sent to the DCC and entered a second time for verification. Forms with personal identifiers are not sent to the DCC; they remain at the clinical site.

7.2 Quality Assurance

The Project Manager/Clinical Monitor will review the data submitted to the DCC for accuracy and completeness. The Project Manager/Clinical Monitor will communicate with the study coordinators at each site about queries generated by the DCC and address all questions and concerns regarding the study protocol and problems with data entry or specimen sample shipment. Site visits will be made approximately every 24 months. Interim site visits may be made to centers with low compliance or high error rates. Performance reports will be generated quarterly to investigators and study coordinators at each center, as well as to DSMB.

7.3 Training

The Project Manager will develop a manual of operations to assist study coordinators at each center in following the protocol, entering and transferring data, and collecting, processing and shipping samples. The Project Manager and Clinical Monitor will be responsible for training the study coordinators at each center about the study protocol, the completion of source documents, the use of the web-based data entry system, and proper procedures with shipping samples to the central repository. Test runs of data entry into the web-based data entry system as well as sample shipment will be organized prior to site initiation. The Project Manager/Clinical Monitor will review the study protocol and data entry system, and check all regulatory documents prior to site initiation. A meeting for all investigators and study coordinators will be held in conjunction with the initiation of the study. In-service training for all study coordinators will be held quarterly via conference calls to review frequently encountered questions regarding the protocol, data entry or sample processing.

8. ADVERSE EVENTS

8.1 Risks

There are minimal physical and psychological risks from participating in this study. Medical risks include those related to the identification or failure of identification of abnormalities or incidental findings on the abdominal ultrasound. These results will be discussed by the study investigators with the patient and family and the patient's care team with further management/referral if necessary directed by the care team. Psychological risks to the family and child include gaining additional knowledge about the child's liver disease or the suggestion of the presence of possible (but unproven) liver disease or about possible associations of family or genetic factors with the child having developed liver disease. The risks of venipuncture for the serum bank are pain, bruising or superficial phlebitis. The risks of genetic information being revealed by any future investigations in the Consortium are very slight since the blood samples will be deidentified prior to being deposited in the repository. If there is a loss of confidentiality, the risks include: that knowledge of a genetic risk may be emotionally stressful to a family member, that this might change eligibility for new health, disability or life insurance, that there may be unforeseen paternity issues, and that genetic testing may reveal information regarding health risks to other members of the family who are living or not yet born. Abdominal Ultrasound is a routine, noninvasive procedure. There are no known risks from performing this procedure. Occasionally, patients may experience mild discomfort from lying still on their back during the examination. All possible techniques for relieving patient discomfort will be attempted. Patients unable to tolerate the examination will be excluded from the study.

